For depressive symptoms, we hypothesize that 25%-35% of participants in the control arm will have a reduced depressive symptom scores (on CES-DC) compared with their baseline score; while about 40-50% participants in the intervention arm will have reduced symptom scores. Table 1 shows the study has a power of >0.80 if the difference between the two study arms is  $\Delta=10\%$  or larger. For HIV/STI acquisition, we power the study based on the outcome of any HIV/STI infection (which we expect to be primarily driven by

change from baseline. Including data from all study visits and adjusting for baseline covariates will potentially increase study power to detect difference between the intervention and control.

**Language.** All study materials and procedures will be conducted in English or isiXhosa. Study materials will be translated by a professional translator, then back-translated to ensure accuracy. Participants will identify language of preference and multi-lingual research assistants (RAs) will conduct procedures in the preferred language. We draw from our established research networks to hire a team experienced intervention delivery, tracking and tracing, and qualitative research with adolescents and families.

**Site description.** Our trial field site will be at DTHF's Masiphumele community center. This spacious, welcoming facility is ideal for delivery of our interactive family-based intervention, with clinic and lab space to facilitate collection of biosamples for HIV and STIs (for site details, see DTHF's Facilities and Resources). We will move to telephonic delivery of the intervention as an option during the COVID-19 crisis.

**Characteristics of the Study Population.** We aim for an initial sample size of N=880 adolescent-parent dyads (n=880 adolescents and n=880 parents) for the intervention. Participants will be recruited from the community setting (Masiphumele Community Center and surrounding community. This site has high HIV prevalence and are primarily black African (99%) and isiXhosa speakers (96%).

**Inclusion and Exclusion Criteria.** We use the following **eligibility criteria** to recruit families into the intervention. Please note that criteria for inclusion of parents was changed from the original grant submission based on critiques of reviewers and requests from NIH. Now parent inclusion criteria reflect more flexibility.

Adolescent inclusion criteria are:

- 1) 14-16 years;
- 2) concurs that the adult identified is their parent (to also include primary caregivers in the parental role);
- 3) when more than one child in the family falls within the eligible age range, one child will be chosen at random;
- 4) lives in the household at least 4 days a week; and
- 5) sub threshold depressive symptoms (score 6-15) using the CES-DC (child version).

Adolescents will be excluded if:

- 1) they report no or low symptoms (<6) or clinically significant thresholds of depression (16+);
- 2) If any or both in the adolescent-parent dyad are unwilling to consent and/or assent.

Parent inclusion criteria are:

- 1) 18+ years,
- 2) parent or equivalent person responsible (as identified by the household);
- 3) when more than one parent who provides primary care exists in the household, one will be chosen at random to ensure consistency in intervention activities;
- 4) lives in the household at least 4 days a week; and
- 5) sub threshold depressive symptoms (score 0-15) using the CES-D Revised (adult version).

Parents will be excluded if:

- 1) they report clinically significant thresholds of depression (16+);
- 2) If any or both in the adolescent-parent dyad are unwilling to consent and/or assent.

We do not exclude participants based on ethnicity, population, or language groups, but expect that due to the demographics of our study area, we are likely to enroll predominantly isiXhosa, Black African participants. For adolescents, our intervention focuses on preventing HIV risk behavior so adolescents can be sexually active or inactive. We would also like to clarify that our study is not a treatment study and as such, does not enroll psychiatric patients. Instead we focus on individuals that are not meeting clinically significant levels of depressive symptomology based on self-report because this behavioral intervention has a preventive focus. Because we use self-report and non-clinician administered measures to assess possible depressive symptoms, and as such we are not diagnosing mental illness, we will provide a list of clinics where individuals who meet clinically significant levels of depressive symptomology based on self-report so they can be evaluated by mental health professionals. The target population is served by South Africa's public health system, where services are provided for free at point of service.

**Inclusion of Minors.** This study includes adolescents who are 14-16 years at baseline, and who may be 17 years of age at the end of this study. This population is considered a vulnerable populations. Inclusion of this population is justifiable; conducting research with this population is necessary in order to develop and test evidence-based programs for adolescent HIV risk and depression preventive interventions. This age group was chosen to because these children are entering an age range in which they will be engaging in HIV risk behaviors and elevated risk for depression. As such, they are ideal for a preventive-focused intervention. We recognize that children may be a vulnerable group, and extreme care is required to ensure protection of these participants. Our investigative team has extensive experience in working with adolescents, particularly in regards to mental health and HIV. Because the development and testing of our preventive intervention involves both parents and adolescents, both parents and children provide informed consent and informed assent respectively. All consent and assent forms will be read aloud in participants' chosen language and participants will also be provided copies. Voluntary informed consent (for adults) and voluntary informed assent (for adolescents) participate only after having read/been read aloud the information sheet and had the opportunity to ask questions. To ensure that children do not feel obliged to participate in the research, emphasis will be placed on their ability to refuse to participate, or to cease participation at any point during the research. We emphasize that all information shared with us will remain confidential except for disclosures that fall under legally mandated reporting requirements.

**Setting and location.** We will recruit from, and conduct this study in a community setting (to maximize external validity/generalizability of trial results). Recruitment will occur within the community center and also in the surrounding community, via house-to-house sampling. The intervention will occur in the Masiphumele Community Center, in a private space in a building that serves the target population.

### **3. Recruitment and Enrollment**

**Recruitment setting and procedures.** Our trained bi-lingual study team will recruit.

For Aim 1 (efficacy trial), we will recruit N=880 adolescents (and N=880 parents) to test *Our Family Our Future* (described above) in a fully-powered RCT. We will recruit in person through the Masiphumele community site and in the community. We use a recruitment strategy based on "approach all" in both the Masiphumele Community Center (run by the Desmond Tutu HIV Foundation) and surrounding community to limit bias and combat stigma. In the community, we recruit based on procedures used in the preliminary studies. This includes splitting the

Masiphumele community into census enumeration size areas, randomly selecting one area to begin to limit geographical bias. Then, we will systematically recruit by going door-to-door, approaching all for study information and eligibility screening. We visit homes up to 3 times at different times and days to limit day/time bias.

For Aim 2, we do *not* recruit any new participants. This aim is analytical, focusing on the data that was collected in Aim 1.

For Aim 3, For Aim 3 (qualitative component), we recruit a convenience sub-sample of adolescents and parents who were randomized to the intervention arm for in-depth interviews, based on prior participation in the efficacy trial (Aim 1) since planned qualitative interviews in Aim 3, explore the experience of the intervention. The recruitment, consent and assent process for adolescents and parents was described under Aim 1. For stakeholder in-depth interviews, we will recruit individuals that can provide insight into future implementation of the intervention (including intervention facilitators) as well as individuals that may have a stake in future scale-up and implementation of the intervention if shown to be efficacious such as possible future interventionists, program directors, and leadership at DTHF. Stakeholder participants will be recruited through flyers providing contact details for study staff in the community organization work areas. We will also recruit using an initial participant seed pool as recommended by Drs. [name] and [name]. These stakeholders will identify other stakeholders. Staff will speak to interested stakeholders privately by phone or in person. Then study staff will obtain informed voluntary consent.

**Eligibility Assessment, Enrollment, and Randomization.** The study staff will assess *eligibility*. Eligibility for parents and eligibility for adolescents will be individually determined. Eligibility will be auto-calculated using a pre-programmed computerized method using our secure mobile project-dedicated android phones or “survey devices” that are part of our field-based data collection system (see details on SurveyToGo software used for data collection). The survey devices will automatically calculate eligibility based on the inclusion/exclusion criteria outlined above. Final eligibility will be determined by dyadic eligibility (that is both parents and adolescents have to be eligible to be invited to participate in this family-based intervention). Eligible parent-adolescent dyads will be invited to participate in the baseline assessment and attend an enrollment session where randomization will occur. If interested, each individual in the dyad will be go through individualized informed consent and assent processes. After completing baseline data collection, each individual in the dyad will be issued matching “invitation tickets” to attend the enrollment session. Invitation tickets provide participants with date and location of the enrollment session. These invitation tickets also display unique ID numbers to allow us to verify at the enrollment session that we have screened individuals for eligibility (by matching unique ID numbers on the ticket with our data system) and help us ensure scheduling of dyads. Dyads will attend an enrollment session where trained study staff will answer questions about the study. Following this information session, study staff will gather voluntary informed consent and assent forms from interested individuals. If consent and assent are obtained for a complete dyad, trained study staff will use a computerized block randomization procedure using our FileMaker Software which automatically determines dyad assignment to the intervention or control group based on programming out [name] and our data team. The block randomization procedure will balance allocation dyads for adolescent gender. Dyads assigned to the intervention group will receive the first intervention session that same day. Dyads assigned to the control group will be given usual care (consisting of a packet of existing available brochures on HIV, STIs, mental health including places to access care). Because randomization occurs in a group setting, assignment is not concealed from participants or from study staff who are part of the intervention team or fidelity

team. However, assignment will be concealed from study staff who are part of the outcomes assessment team (single-blind) so as not to affect assessment of hypothesized effects of the intervention.

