3. **Identify barriers and facilitators to implementing *Our Family Our Future* within a community-based organization setting to provide data for future dissemination (presuming *Our Family Our Future* is efficacious).** We examine processes critical to future dissemination through (a) fidelity data examining adherence to core active components of the standardized intervention manual guiding consistent delivery of the intervention; and (b) qualitative data on the experience during and post-implementation from adolescents, families, and stakeholders using N=30-45 in-depth interviews.

The expected outcomes of this study includes efficacy data for the first integrated family intervention for prevention of adolescent HIV/STIs with depression in a community setting, and data to inform future dissemination, implementation, and scale-up.

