**Aim 3 - In-depth interview procedures.** Interviews will last 1 to 1.5 hours and take place in a private room at University of Cape Town or in the community intervention site. Due to the COVID-19 crisis, we will default to interviews by phone as needed. Sociodemographic and behavioral data will be gathered during Aim 1. We use a semi-structured agenda to guide qualitative interviews organized by exemplar key questions; exact wording will vary depending on language and cultural norms and will explore these themes: (1) barriers and facilitators to attendance and intervention participation, particularly in relation to scale-up and implementation; (2) acceptability of intervention strategy; (3) predicted behavioral impacts of intervention content including areas that need further refinement and strengthening; (4) advice on format, frequency, timing, and delivery aspects to facilitate future scale-up and dissemination; (5) organizational considerations including advice on gaining buy-in from key gatekeepers; (6) open solicitation of other key considerations for future dissemination, scale-up, and implementation. We record interviews using a digital voice recorder (DVR). At the close of each interview, we will thank participants and provide reimbursement.

**Assessment Procedures.** Well established measures with good reliability and validity were piloted in the preliminary studies.

Table 2: Outcome Measures and Assessment Timeline				
Outcome	Measures	Baseline	3-mth	12-mth
HIV Risk Behavior & Intentions: biologically verified HIV, STIs; prior and planned pregnancy and contraception; sex	• Items taken from South African trials & NIH's Adolescent Medicine Trials Network for HIV/AIDS Interventions; Sexual Experiences Survey 	✓	✓	✓

frequency; partner number; condom use; sex refusal				
Depression: depression symptom severity	• Center for Epidemiologic Studies Scale - Revised (CESD-R) adult and child versions 	✓	✓	✓
Co-variates: socio-demographics; economic status; household characteristics	• Items from the South African Census Questionnaire, World Health Organization Food Security Questionnaire;  Verbal Symptom and Autopsy Questionnaire for HIV illness and AIDS orphanhood 	✓	✓	✓

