We investigate fidelity assessments (coding a minimum of 15% of sessions), we follow recommendations issued by the Treatment Fidelity Workgroup of the NIH Behavior Change Consortium to ensure coding of fidelity based on a standardized monitoring checklist to assess: 1) facilitator adherence/drift from fidelity. These fidelity assessment will be gathered in real time, as intervention facilitators deliver the intervention. We will also gather data to understand attrition which gives us information on another aspect of feasibility. This will include gathering characteristics on who is eligible (from baseline data) but does not attend the enrollment session; data on who fills out baseline, post-, and 3 month assessments; as well as who attends scheduled intervention sessions. We gather process data including data on treatment integrity by examining the rigor of the intervention implementation to the standardized manualized protocol through fidelity data. Fidelity coding will be conducted on 10-15% of total sessions using a neutral coder, ranking integrity and competency of session delivery in real time, and following recommendations issued by the Treatment Fidelity Workgroup of the NIH Behavior Change Consortium^157 We also track recruitment, retention, and attrition data using FileMaker Software to identify ways for optimization of the intervention in future dissemination, implementation, and scale-up should it show efficacy. This will include gathering characteristics on who is eligible (from baseline data) but do not attend the enrollment session as well as who attends scheduled intervention sessions. For process data we recruit adolescents, parents, and stakeholders including representatives from DTHF, a well-established community organization that is an ideal target for future scale-up and implementation research for in-depth interviews (N=30-45) with final sample size is based on data saturation. We anticipate these assessments will take 10 minutes. We also gather process data through qualitative in-depth interviews in Aim 3. All measures are provided for full review. There will be no additions to the questionnaire (see Appendix) without approval of the IRB, although some questions may be cut to reduce survey length after piloting.

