Cons of participation	4 – Discuss last cons of enrolling in the study	1 – Discuss first cons of not enrolling in the study

The idea of this behavioral run-in is to provide a more in-depth orientation session after participants have been given time to consider the study in depth (following an initial consent and assent at baseline). In this behavioral run-in, we provide a thorough discussion of ethical considerations to complement traditional consent/assent procedures. This discussion focuses upon eliciting potential participants’ perspectives of pros and cons of their potential trial enrollment to help them consider risks and benefits thoroughly, to explicitly acknowledge study challenges, and to engage in a meaningful interactive dialogue to overcome any misunderstandings of the study (including confusion on trial design and objectives, prevention misconception, and other ethical challenges documented by studies on related topics in similar settings). The approach avoids a “hard sell” or “pro-change” positions, but instead, focuses on enriching the informed consent and assent process to ensure meaningful informed and voluntary consent and

assent. This second stage consent and assent process includes an option for choosing to participate in Aim 3 for adolescents and participants. For Aim 3 stakeholder in-depth interview participants, we will secure written voluntary informed consent before proceeding with interviews.

**Consent Form Labeling.** We learned a great deal in preliminary studies about designing a family friendly program including naming of materials. This issues of HIV-fatigue and stigma of both HIV and depression were highlighted suggesting that the program name should not include these terms. Aim 1 participants describes a family friendly program and generated possible program names which emphasized family empowerment, unity, and learning in the program name. As such, we have chosen to prominently reflect a positive program name in the study materials (recruitment, outreach, consent and assent forms, etc.) and not to use the scientific study name to increase acceptability with the target study population and in the study community. We come up with the program name of, "Our Family Our Future" based on concepts and words identified preliminary studies.

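### Aim 3 asks families about barriers to attendance, but its convenience sample of intervention-arm families need not include any who stopped attending

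*Combined protocol and SAP*

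**What the plan says.** The third specific aim (Study Aims) is to "Identify barriers and facilitators to implementing" the programme in a community organisation, so as to inform dissemination. It uses fidelity data and 30-45 in-depth interviews with adolescents, families and stakeholders. Under Aim 3 - In-depth interview procedures (section 4), the first of six themes is "barriers and facilitators to attendance and intervention participation, particularly in relation to scale-up and implementation".

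The family interviewees are defined under Recruitment setting and procedures (section 3): "we recruit a convenience sub-sample of adolescents and parents who were randomized to the intervention arm for in-depth interviews". The stated basis is "based on prior participation in the efficacy trial (Aim 1) since planned qualitative interviews in Aim 3, explore the experience of the intervention". No quota or stratum by attendance or delivery format is set. Stakeholders, including the intervention facilitators, are recruited separately.

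The route into the intervention arm is in the same section, under Eligibility Assessment, Enrollment, and Randomization. Eligible dyads are invited to "attend an enrollment session where randomization will occur", and those allocated to the intervention are given session 1 on that day. Section E offers the Aim 3 choice at that stage, before randomisation: "This second stage consent and assent process includes an option for choosing to participate in Aim 3 for adolescents and participants".

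On attrition, section 4 (Assessment Procedures) plans to record who misses enrollment and who comes to the programme's later sessions: "This will include gathering characteristics on who is eligible (from baseline data) but do not attend the enrollment session as well as who attends scheduled". The final number of interviews depends on saturation (sections 4 and 6). Interviews take place at the university or the intervention site, with telephone as needed because of COVID-19.

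**The concern.** A family that stopped after the first session, or missed later ones, can explain at first hand what stood in the way. A convenience sample leaves it to chance whether such families are interviewed. Those who are easy to reach and willing to come to the site may also be those who found the sessions easy to attend. The pilot's attendance problems included travel cost and safety on the way to the site (Background), and the same obstacles could keep a family from an interview held there.

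Saturation does not guard against this. If most interviewees kept attending, their themes can stop yielding anything new while the reasons of those who left remain unheard. What is at stake is the usefulness of Aim 3 for dissemination: the report could list the barriers that families overcame and miss some that stopped them. The Aim 1 efficacy comparison does not depend on these interviews.

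**Working it through.** The plan states no figure to reproduce. It gives no attendance rate (the Background describes pilot attendance only as good on average), no split of the interviews between families and stakeholders, and no expected number of low attenders. The check has two parts.

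**1. Who can be interviewed, from the plan's own flow**

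| Group | In the interview frame? | What the plan will learn |
|---|---|---|
| Eligible, did not come to the enrollment session | No, never randomised | Characteristics only |
| Intervention arm, stopped or missed sessions after the first | Yes, but not sought out | Attendance record; own reasons only if picked by chance |
| Intervention arm, telephone delivery | Yes, but not sought out | Own views only if picked by chance |
| Intervention arm, kept attending | Yes | Own views |

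In the in-person flow, then, every family in the frame came at least once. Telephone delivery during COVID-19 could loosen that link.

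**2. How many low attenders might be interviewed (illustration)**

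All three inputs are assumptions:

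- q, the share of low attenders among intervention families: 10% to 30%.
- r, a low attender's chance of being interviewed relative to that of other families: 0.25 to 0.5.
- m, the number of family interviews: two thirds of the total, so 2/3 × 30 = 20 to 2/3 × 45 = 30.

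The probability that one interview is with a low attender is p = qr / (qr + 1 − q). The expected number is m × p. The probability of none is (1 − p)^m, treating interviews as independent draws.

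Lowest corner: p = 0.10 × 0.25 / (0.025 + 0.90) = 0.027, and 20 × 0.027 = 0.5. Highest corner: p = 0.30 × 0.5 / (0.15 + 0.70) = 0.176, and 30 × 0.176 = 5.3.

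| q | r | m | p | Expected | P(none) |
|---|---|---|---|---|---|
| 0.10 | 0.25 | 20 | 0.027 | 0.5 | 0.58 |
| 0.20 | 0.25 | 20 | 0.059 | 1.2 | 0.30 |
| 0.20 | 0.5 | 20 | 0.111 | 2.2 | 0.09 |
| 0.20 | 0.5 | 30 | 0.111 | 3.3 | 0.03 |
| 0.30 | 0.5 | 30 | 0.176 | 5.3 | <0.01 |
| 0.20 | 1 (no selection) | 20 | 0.200 | 4.0 | 0.01 |
| 0.20 | 1 (no selection) | 30 | 0.200 | 6.0 | <0.01 |

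The last two rows show that part of any shortage would come from the small group size and part from selection. A minimum share addresses both. With a share of one third, for example, the number is fixed at about 7 of 20 (20/3 = 6.7) or 10 of 30. The pool should be large enough: at q = 10%, 440 intervention families would include 44 low attenders, though not all will have opted into Aim 3.

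**The case against.** A reader might infer that the interviewees will mostly be families who kept attending. The documents do not say so. The frame is families randomised to the intervention, and the stated basis is participation in the trial, not attendance at sessions. Families who left after session 1 are eligible, and they can have opted in before attendance diverged. The Retention paragraph (section 4) keeps enrolled families traceable through several contacts, monthly calls or texts, geo-location, and home or telephone follow-up. The pilot reports 100% retention at 1 and 3 months. All this shows that low attenders can be found. It does not show that anyone is asked to interview them.

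A reader might also infer, from the pilot's uniformly high satisfaction, that attenders do not report barriers. The Background contradicts that. Pilot families named sessions ending after dark, incomplete travel reimbursement, food, fixed groups and an unsafe site. People who took part can therefore describe barriers. Whether these were the barriers that made others stop is not known.

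Further points in the plan's favour stand in part. Attendance belongs to one of six themes in an exploratory component. The sample is openly labelled a convenience sample, and a reason is given. Facilitators can report what they heard, but only at second hand. Attrition tracking shows who stayed away; it plans to record characteristics and attendance, not reasons.

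**Conclusion.** The point holds as a gap in sampling. The plan asks about barriers to attendance and does nothing to ensure that families who stopped attending, or who had telephone delivery, are among those asked. Under the assumed ranges, about 0.5 to 5 low attenders would be expected among 20-30 family interviews, and the chance of interviewing none runs from under 1% to 58%. These figures rest wholly on assumed inputs. They show how much is left to chance and do not predict the sample. The documents set no number of low attenders that would be enough, so no claim is made that a given count falls short of saturation.

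The documents do not support the stronger conclusion that Aim 3 will fail to find attendance barriers, given the pilot feedback and the facilitator interviews. Those sources soften the gap without supplying the reasons of the families themselves. This is a worthwhile, inexpensive improvement to Aim 3, with no bearing on Aim 1.

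**What to change.** - **Section 3, Recruitment setting and procedures (Aim 3).** Replace convenience selection of families with purposive sampling from the attendance data already tracked in FileMaker. Set a minimum share of families who missed one or more sessions after the first (for example one third) and a minimum for each delivery format, group and telephone.
- **Sections 4 and 6, saturation.** Judge saturation on the attendance theme within the low-attendance group as well as overall.
- **Section 4, Aim 3 interview procedures.** Allow telephone interviews for these families whether or not COVID-19 restrictions apply.
- **Reporting.** State that Aim 3 conclusions on attendance barriers do not cover eligible families who never came to the enrollment session. Only their characteristics are recorded, and sampling within the intervention arm cannot reach them.

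The total stays at 30-45 interviews. Attendance records, contact details and the Aim 3 consent option are already in place, so the change is a few sentences of protocol text. The cost is some extra tracing and a slower fill of the interview places.
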